**Figure 1. Study Design**

Participants will be required to complete a daily seizure calendar noting seizure type and frequency in an electronic seizure diary calendar to determine GNX's effect on drug resistant seizures.

The Schedule of Events for the 17-week pre-randomization and double-treatment phase is presented in [Table 1](#). The Schedule of Events for the OLE is presented in [Table 2](#).

**Table 1: Schedule of Assessment for the 17-week, Double-blind Treatment Phase of the Study**

	Screen/Baseline			DB Titration + Maintenance					Final DB Visit
WEEK	-14	-6 (Screening)	0 Baseline (Randomization)	3 days	1, 2, 3, 4	5	9	11, 13	17
Visit Windows			+6 days n	± 1 day	± 3 days	± 3 days	± 3 days	± 3 days	± 3 days
	Historical Seizure frequency	Visit 1	Visit 2	Phone Follow-up	Phone Follow-up	Visit 3	Visit 4	Phone Follow-up	Visit 5
Screening and Diagnosis									
Informed Consent a	X b	X							
Demographics & Medical History		X	X c						
Historical Seizure Calendar Review		X							
Inclusion/Exclusion Criteria		X	X						
Genetic testing d		X							
Seizure Identification and Diagnostic Review Form (Epilepsy Study Consortium)		X	X						
Safety Assessments									
Vital signs (BP, HR, RR, and body temperature)		X e	X			X	X		X f
Physical/Neurological/Developmental Exam		X				X			X
Physical/Neurological/Developmental Exam Follow-up			X				X		

**Table 1: Schedule of Assessment for the 17-week, Double-blind Treatment Phase of the Study**

WEEK	Screen/Baseline			DB Titration + Maintenance					Final DB Visit
	-14	-6 (Screening)	0 Baseline (Randomization)	3 days	1, 2, 3, 4	5	9	11, 13	17
Visit Windows			+6 days n	± 1 day	± 3 days	± 3 days	± 3 days	± 3 days	± 3 days
	Historical Seizure frequency	Visit 1	Visit 2	Phone Follow-up	Phone Follow-up	Visit 3	Visit 4	Phone Follow-up	Visit 5
ECG		X	X			X			X
Clinical Laboratory Tests g		X	X			X	X		X
Urinalysis		X h	X h						X
Drug screen i		X							
Pregnancy Test (WCBP) j		X	X						
Tanner Staging		X							
Investigational Product PK						X k	X k		X
Concomitant AED Review and levels if per standard of care l		X	X			X	X		X
Neurosteroid levels		X							X
Adverse Event		X	X	X	X	X	X	X	X
Efficacy Assessments									
Seizure eDiary review		X	X	X	X	X	X	X	X
Caregiver Global Impression of Change in Attention (CGICA)		X m				X	X		X
Caregiver Global		X m				X	X		X

**Table 1: Schedule of Assessment for the 17-week, Double-blind Treatment Phase of the Study**

	Screen/Baseline			DB Titration + Maintenance					Final DB Visit
WEEK	-14	-6 (Screening)	0 Baseline (Randomization)	3 days	1, 2, 3, 4	5	9	11, 13	17
Visit Windows			+6 days n	± 1 day	± 3 days	± 3 days	± 3 days	± 3 days	± 3 days
	Historical Seizure frequency	Visit 1	Visit 2	Phone Follow-up	Phone Follow-up	Visit 3	Visit 4	Phone Follow-up	Visit 5
Impression of Change in parent/caregiver identified behavioral target (CGI-C)									
Caregiver Global Impression of Change in Seizure Intensity/Duration (CGI-CSID)						X	X		X
Clinical Global Impression Improvement (CGI-I) by parent/caregiver & clinician		X m				X	X		X
			█						█
			█			█	█		█
			█			█	█		█
			█			█	█		█

**Table 1: Schedule of Assessment for the 17-week, Double-blind Treatment Phase of the Study**

	Screen/Baseline			DB Titration + Maintenance					Final DB Visit
WEEK	-14	-6 (Screening)	0 Baseline (Randomization)	3 days	1, 2, 3, 4	5	9	11, 13	17
Visit Windows			+6 days n	± 1 day	± 3 days	± 3 days	± 3 days	± 3 days	± 3 days
	Historical Seizure frequency	Visit 1	Visit 2	Phone Follow-up	Phone Follow-up	Visit 3	Visit 4	Phone Follow-up	Visit 5
			■			■	■		■
Dispense Investigational Product			X			X	X		X

AED = antiepileptic drug; BP = blood pressure; CBD = cannabidiol; D/C = discontinuation; DB = double-blind; ECG = electrocardiogram; EEG = electroencephalogram; HR = heart rate; LAR = legally authorized representative; PK = pharmacokinetic; RR = respiratory rate; THC = tetrahydrocannabinol; WCBP = women of childbearing potential.

- a. Written informed consent/assent must be obtained from subject, parent or LAR before any study assessments are performed.
- b. Written informed consent/assent from subject, parent or LAR needed if 8-week historical control is not available and need to chart prospectively.
- c. Review of medical history only.
- d. Genetic testing to be performed to confirm pathogenic or likely pathogenic CDKL5 variant.
- e. In addition, height and weight will be measured. If weight unable to be collected at Visit 1, may be collected at Visit 2.
- f. In addition, weight will be measured.
- g. Chemistry & Hematology (Section 12.2).
- h. An attempt should be made to collect a urine sample for a urinalysis at screening. Otherwise, the urine sample can be collected at baseline for the urinalysis.
- i. A drug screen (urine or plasma) will be performed to test for THC and CBD at screening. A negative drug test at screening meets the protocol eligibility criteria. If the screening drug test is positive, a plasma drug screen will be performed to test for THC and CBD at baseline. A positive drug test at baseline will exclude the subject from the study.
- j. Serum pregnancy test is required for all girls/women of childbearing potential.
- k. Population PK will be conducted at these visits (Visit 3: between 1-5 hours since last IP dosing, Visit 4: between 4-8 hours since the last IP dosing).
- l. Concomitant AEDs or their dose must be stable for 1 month prior to screening and cannot be changed at any time prior to Visit 5 but may be adjusted during the open-label phase of the study.
- m. During the Screening visit, the investigator and parent/caregiver/LAR will decide on a specific behavior that the patient exhibits that denotes assessment measured. This behavior will be used at subsequent visits to assess change after the initiation of investigational product.
- n. Visit 2 to occur minimum of 6 weeks (42 days) after Visit 1 and maximum of 6 weeks + 6 days (48 days)

**Table 2: Schedule of Assessments for Open-Label Phase**

	Final DB Visit/ First OL Visit	Titration (4 weeks blinded)					Open-Label Maintenance (Visits will be every 16 weeks with a telephone follow up in-between after 52 weeks)						Final OL Visit or Taper	Safety Follow-up post
WEEK	17	3 Days Post Visit 5	18	19	20	21	28	34	43	52	60	68 and X visit	X/ or early D/C	2 weeks post last
Visit Windows		± 1	± 3 days	± 3 days	± 3 days	± 3 days	± 7 days	± 7 days	± 7 days	± 7 days	± 7 days	± 7 days	± 7 days	± 3 days
	Visit 5	Phone follow-up	Phone follow-up	Visit 6	Phone follow-up	Visit 7	Phone follow-up	Visit 8	Phone follow-up	Visit 9	Phone follow-up	Visit 10 and Visit X	Visit X	Visit X
Safety Assessments														
Vital signs (BP, HR, RR, and body temperature) a	X a			X		X		X a b		X a b		X a	X a b	X
Physical/Neurological/Developmental Exam	X					X		X		X		X	X	
Physical/Neurological/Developmental Exam Follow-up				X										X
ECG	X					X		X		X		X	X	
Clinical Laboratory Tests c	X			X	X	X		X		X		X	X	X
Urinalysis	X									X e			X	X e
Pregnancy Test (WCBP) d													X	X
Tanner Staging e										X			X	

**Table 2: Schedule of Assessments for Open-Label Phase**

	Final DB Visit/ First OL Visit	Titration (4 weeks blinded)					Open-Label Maintenance (Visits will be every 16 weeks with a telephone follow up in-between after 52 weeks)						Final OL Visit or Taper	Safety Follow-up post
WEEK	17	3 Days Post Visit 5	18	19	20	21	28	34	43	52	60	68 and X visit	X/ or early D/C	2 weeks post last
Visit Windows		± 1	± 3 days	± 3 days	± 3 days	± 3 days	± 7 days	± 7 days	± 7 days	± 7 days	± 7 days	± 7 days	± 7 days	± 3 days
	Visit 5	Phone follow-up	Phone follow-up	Visit 6	Phone follow-up	Visit 7	Phone follow-up	Visit 8	Phone follow-up	Visit 9	Phone follow-up	Visit 10 and Visit X	Visit X	Visit X
Investigational Product PK	X			X		X f		X		X f		X	X	X
Concomitant AED Review and levels if per standard of care	X			X		X		X		X		X	X	X
Neurosteroid Levels	X												X	
Adverse Event	X	X	X	X	X	X	X	X	X	X	X	X	X	X
Efficacy Assessments														
Seizure eDiary review	X	X	X	X	X	X	X	X	X	X	X	X	X	X
Caregiver Global Impression of Change in Attention (CGICA)	X					X		X		X		X	X	

**Table 2: Schedule of Assessments for Open-Label Phase**

	Final DB Visit/ First OL Visit	Titration (4 weeks blinded)					Open-Label Maintenance (Visits will be every 16 weeks with a telephone follow up in-between after 52 weeks)						Final OL Visit or Taper	Safety Follow-up post
WEEK	17	3 Days Post Visit 5	18	19	20	21	28	34	43	52	60	68 and X visit	X/ or early D/C	2 weeks post last
Visit Windows		± 1	± 3 days	± 3 days	± 3 days	± 3 days	± 7 days	± 7 days	± 7 days	± 7 days	± 7 days	± 7 days	± 7 days	± 3 days
	Visit 5	Phone follow-up	Phone follow-up	Visit 6	Phone follow-up	Visit 7	Phone follow-up	Visit 8	Phone follow-up	Visit 9	Phone follow-up	Visit 10 and Visit X	Visit X	Visit X
Caregiver Global Impression of Change (CGI-C) in parent/caregiver identified behavioral target	X					X		X		X		X	X	
Clinical Global Impression of Improvement (CGI-I) by parent/ caregiver & clinician)	X			X		X		X		X		X	X	
Caregiver Global Impression of Change in Seizure Intensity/Duration Severity (CGI-CSID)	X					X		X		X		X	X	

**Table 2: Schedule of Assessments for Open-Label Phase**

	Final DB Visit/ First OL Visit	Titration (4 weeks blinded)					Open-Label Maintenance (Visits will be every 16 weeks with a telephone follow up in-between after 52 weeks)						Final OL Visit or Taper	Safety Follow-up post
WEEK	17	3 Days Post Visit 5	18	19	20	21	28	34	43	52	60	68 and X visit	X/ or early D/C	2 weeks post last
Visit Windows		± 1	± 3 days	± 3 days	± 3 days	± 3 days	± 7 days	± 7 days	± 7 days	± 7 days	± 7 days	± 7 days	± 7 days	± 3 days
	Visit 5	Phone follow-up	Phone follow-up	Visit 6	Phone follow-up	Visit 7	Phone follow-up	Visit 8	Phone follow-up	Visit 9	Phone follow-up	Visit 10 and Visit X	Visit X	Visit X
[REDACTED]	■					■		■		■		■	■	
[REDACTED]	■					■		■		■		■	■	
[REDACTED]	■					■		■		■		■	■	
[REDACTED]	■					■		■		■		■	■	
Dispense Investigational Product	X			X		X		X		X		X	X	

**Table 2: Schedule of Assessments for Open-Label Phase**

	Final DB Visit/ First OL Visit	Titration (4 weeks blinded)					Open-Label Maintenance (Visits will be every 16 weeks with a telephone follow up in-between after 52 weeks)						Final OL Visit or Taper	Safety Follow-up post
WEEK	17	3 Days Post Visit 5	18	19	20	21	28	34	43	52	60	68 and X visit	X/ or early D/C	2 weeks post last
Visit Windows		± 1	± 3 days	± 3 days	± 3 days	± 3 days	± 7 days	± 7 days	± 7 days	± 7 days	± 7 days	± 7 days	± 7 days	± 3 days
	Visit 5	Phone follow-up	Phone follow-up	Visit 6	Phone follow-up	Visit 7	Phone follow-up	Visit 8	Phone follow-up	Visit 9	Phone follow-up	Visit 10 and Visit X	Visit X	Visit X

AED = antiepileptic drug; BP = blood pressure; DB = double-blind; D/C = discontinuation; ECG = electrocardiogram; EEG = electroencephalogram; HR = heart rate; PK = pharmacokinetic; OL = open-label; RR = respiratory rate; WCBP = women of childbearing potential.

- a. In addition, weight will be measured at every visit, except the safety follow-up visit.
- b. In addition, height will be measured. Height will be measured annually after Visit 9 (Week 52), except the safety follow-up visit.
- c. Chemistry & Hematology ([Section 12.2](#)).
- d. Serum pregnancy test is required for all girls/women of childbearing potential.
- e. Conduct annually and at the final open-label visit.
- f. Population PK will be conducted at these visits: Visit 7: between 1-5 hours since last IP dosing and Visit 9: between 1-5 hours since last IP dosing

### 1.3.2 Sample Size and Statistical Power Considerations

Based on data from the 7 patients in Study 1042-0900 evaluating GNX in CDKL5 patients, the standard deviation for the percent change in 28-day seizure frequency for seizure types tonic (sustained motor activity  $\geq 3$  seconds), tonic-clonic, atonic/drop, epileptic spasms, or clonic (generalized or unilateral) is estimated to be 44.5. Therefore, when the percent change in 28-day seizure frequency on GNX minus that on PBO truly is 30%, then a trial with 100 subjects randomized in a 1:1 manner will have 92% power to detect this effect when using an ANOVA that preserves a (one-sided) 2.5% false positive error rate. If the true difference in the percent changes is 35%, then the study will have 97.5% power.

The threshold for achieving statistical significance at the final analysis when 100 subjects have completed their 17-week DB treatment phase would be an estimate of the difference that is approximately 17.5%. (The actual analysis will use a Wilcoxon rank-sum test, which has approximately the same power as the ANOVA.)

## 2. STATISTICAL METHODS

### 2.1 General Considerations

In general, non-categorical variables will be summarized by number of subjects, mean, standard deviation (SD), median, 25th and 75th percentiles, minimum, and maximum values. Categorical variables will be summarized by counts and percentage of subjects in each category.

Except where noted, separate tables and data listings will be prepared for the DB and OLE phases of the study. Only events occurring before entry into the OLE phase will be included in the DB phase outputs, and except where indicated, only pre-treatment events and events occurring after entry into the OLE phase will be included in the OLE phase outputs. The tables for the DB phase will show the results for each DB treatment group, and, where noted, combined over the groups as well. The tables for the OLE phase will show the results for each DB treatment group (all subjects will be receiving GNX in the OLE phase) and combined over them. For the efficacy endpoints, the results will be derived according to the randomized treatment group; for the other endpoints, they will be derived according to the treatment actually received.

Source data for the summary tables and statistical analyses will be presented as subject data listings, which include data collected on the electronic case report forms (eCRFs) as well as any derived efficacy variables for all enrolled subjects.

Baseline seizure activity will be determined by 6 weeks of prospective recording in subject daily seizure calendars, which are provided after signing informed consent. Within the DB phase of the study, post-baseline seizure activity will be determined by the days following the first day after the first DB treatment. (The first day of DB treatment is included in neither the baseline nor DB phase since seizures could occur both before and after the initiation of treatment.) Within the OLE phase, post-baseline seizure activity will be determined by the first day of OLE treatment.

Baselines for non-seizure efficacy and safety assessments are defined as the last non-missing value of the assessment before the first dose of treatment.

The OLE phase will use the same baseline as the DB phase.

The study day for all assessments that are performed on or after the first day of treatment will be calculated as:

Study Day = date of the assessment – date of first treatment + 1.

For assessments performed before the first day of treatment, the study day calculation is:

Study day = date of the assessment – date of first treatment.

### 2.1.1 Reporting Precision

Summary statistics will be presented to the following degree of precision, unless otherwise specified:

Statistics	Degree of Precision
Mean, Median, Quartiles, Confidence limit boundaries	One decimal place more than the raw data.
Standard deviation	Two decimal places more than the raw data.
Minimum, Maximum	The same as the raw data.
p-value	Rounded to 4 decimal places and therefore presented as 0.xxxx; p-values smaller than 0.0001 as '< 0.0001'; p-values greater than 0.9999 as '> 0.9999'.
Percentage	One decimal place. A percentage of 100% will be reported as 100%. Percentages of zero will be reported as 0.

For weight and height, one decimal place will be used for summary statistics. Fractional numeric values will be presented with a zero to the left of the decimal point (for example, 0.12 - 0.30).

## 2.2 Definitions of Analysis Populations (Analysis Sets)

### 2.2.1 Safety and Intention-to-Treat (ITT) Population

This population comprises all randomized subjects who received at least one dose of study drug. In addition to being the population for the safety analyses, it is the primary population for the efficacy and neurosteroid level analyses.

### 2.2.2 Per-Protocol Population (PP)

This population consists of ITT subjects who received study drug for at least 6 weeks, provided at least 5 weeks of post-baseline seizure data, and had no major protocol violations. There will be no PP population for the OLE phase of the study.

## 2.3 Time Windows for Analysis

For by-visit safety or efficacy summaries, only scheduled visits will be analyzed. But if subjects prematurely discontinue from the study and complete assessments at the Taper Visit, then that visit may be reassigned to another visit for analysis purposes, as described in subsequent sections, including [Section 7.1.1](#).

## 2.4 Pooling of Centers

Data of all sites will be pooled together for analysis.

## 2.5 Handling of Missing Data

Missing data will not be replaced except as noted. Missing efficacy data will be imputed in a sensitivity analysis as described in [Section 7.1.7](#).

## 2.6 Analysis Software

All summaries and statistical analyses will be generated using SAS® version 9.4 or later.

# 3. STUDY SUBJECTS

## 3.1 Disposition of Subjects

A data listing of Screening failures for the DB phase of the study will be provided.

Disposition will be summarized within the DB treatment groups and overall among all subjects within both the DB and extension phases of the study.

The disposition will include the following:

- Subjects screened (DB phase only)
- Screen failures (DB phase only)
- Subjects enrolled (randomized)
- Subjects in the Safety Population
- Subjects in the ITT Population
- Subjects in the PP Population
- Ongoing subjects (OLE phase only)
- Subjects who completed the phase
- Subjects who discontinued study drug before the end of the phase (DB phase only)
- Reasons for study drug discontinuation before the end of the phase (DB phase only)

- Subjects who discontinued study before the end of the phase
- Reasons for study discontinuation before the end of the phase (OLE phase only)

Subjects completing the DB phase of the study are those who completed the 17-week DB treatment phase, regardless of whether they entered the OLE. A listing of dispositions will be provided for all randomized subjects.

### **3.2 Eligibility Criteria and Protocol Deviations**

The clinical team will identify deviations and the deviations will be recorded into the database and provided in a data listing.

A data listing of subjects who violate any of the inclusion/exclusion characteristics will be provided as well as a data listing of subjects with other protocol violations.

## **4. DEMOGRAPHICS AND BASELINE CHARACTERISTICS**

Demographic data (age, gender, race, height, weight and body mass index (BMI), country, and ethnicity) and the Tanner staging collected prior to the first dose; and the number of prior medications taken and stopped prior to the first dose will be summarized using descriptive statistics in the safety population and, if it differs substantially from the safety population, the PP population as well. (The safety population is also the ITT population.) The statistics will be shown within each DB treatment group and combined over them.

Height (in cm) = Height (in inches) \* 2.54

Weight (in kg) = Weight (in lbs) \* 0.4536

BMI (kg/m^2) = Weight (kg)/[Height(m)]

Baseline values of the efficacy and safety parameters will be summarized in the respective tables.

## **5. MEDICAL HISTORY AND GENETIC TESTING**

Medical history will be coded with the Medical Dictionary for Regulatory Activities (MedDRA) Terminology version 16.0 or higher. The number and percent of subjects with clinically significant medical history at screening will be summarized by system organ class (SOC) and preferred term (PT) by treatment and overall in the safety population and, if it differs substantially from the safety population, the PP population as well.

The number and percent of subject replies to each question of the genetic testing done at Screening will be summarized by treatment and overall in the safety population and, if it differs substantially from the safety population, the PP population as well.

## 6. PRIOR AND CONCOMITANT MEDICATIONS AND THERAPIES

Prior medications are defined as medications/therapies that started and stopped prior to the first dose of DB study drug. Concomitant medications/therapies are defined as medications/therapies (other than the study drug) administered on or after the first dose of the DB study, regardless of when the medications/therapies started. The summary of concomitant medications/therapies for the main 17-week DB treatment phase of the study will not include concomitant medications/therapies that start after that phase; i.e., they will not include any starting on or after the first dosing day of the OLE phase.

The summary of concomitant medications/therapies for the OLE phase will include all medications/therapies, other than study drug, administered on or after the first dosing day of the phase. (There will be no summary of prior medications/therapies for the OLE phase.)

All investigator terms for medications recorded on the CRF will be coded using the World Health Organization (WHO) Anatomical Therapeutic Chemical (ATC) drug dictionary (Version WHO Drug Dictionary, March 2014). The number (percentage) of subjects who took prior and concomitant medications will be summarized by treatment and overall in the safety population and, if it differs substantially from the safety population, the PP population as well, by ATC Classification and WHO Drug PT. The tables of prior and concomitant medications will be provided separately for non-AED and AED medications, as will subject data listings of them.

The number (percentage) of subjects who received prior and concomitant therapies will be summarized by treatment and overall in the safety population and, if it differs substantially from the safety population, the PP population as well. The therapies will also be in a subject data listing.

To define prior or concomitant medications/therapies, the following table describes how missing date information will be handled; however the actual dates, not the imputed ones, will display in the listing.

Partial Missing Start or Stop Date	Imputed Start Date	Imputed Stop Date
Missing year, month, and day	First dose date	
Missing month and day, and the year is present	First dose date if the year is the same as the year of first dose date, else first dose date of the OLE if the year is the same as the year of the first OLE dose date, else January 1 of the start year.	December 31 of that year

Missing day, but year and month are present	First dose date if the year and month are the same as the year and month of first dose date, else first dose date of the OLE if the year and month are the same as the year and month of the first OLE dose date, else the 1st of the start month.	Last day of that month
Missing month, but year and day are present	Assume day is also missing and impute as above	Missing month imputed as December

If an imputed start date is later than the stop date, then the stop date (after any needed imputations) will be used instead for the imputed start date.

## 7. EFFICACY ANALYSES

In addition to the descriptive statistics mentioned in [Section 2.1](#), the baseline, post-baseline, and relevant changes from baseline for the seizure endpoints will also be summarized with 95% distribution-free confidence intervals for the median and Hodges-Lehmann point estimates and asymptotic 95% confidence limits for the location shifts. [Section 12.2](#) contains SAS code for obtaining the distribution-free confidence limits for the median and the Hodges-Lehmann estimates and confidence intervals.

The baseline, post-baseline, and changes from baseline for the other non-categorical endpoints will be summarized with 95% confidence intervals for the means and differences in means between the treatment groups in addition to the other descriptive statistics.

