and caregiver administered instruments will be used to assess the efficacy of GNX in CDKL5, and include: Caregiver Global Impression of Change in Attention (CGICA), Caregiver Global Impression of Change (CGI-C) in parent/caregiver identified behavioral target- potential domains of sociability, communication, irritability, and hyperactivity, Clinical Global Impression of Improvement (CGI-I) by parent/caregiver and clinician, Caregiver Global Impression of Change in Seizure Intensity/Duration (CGI-CSID), Children's Sleep Habit Questionnaire (CSHQ), ADAMS, QI-Disability and PSI.

Inclusion and Exclusion criteria:

Inclusion Criteria:

1. (a) Molecular confirmation of a pathogenic or likely pathogenic CDKL5 variant, early onset, difficult to control seizures, and neurodevelopmental impairment are required. The principal investigator (PI) must review the results of the genetic analysis and confirm that gene mutation is likely to be the cause of the epilepsy syndrome. If the subject has a *de novo* variant of unknown significance (VUS) in the kinase domain of the CDKL5, parental testing is negative and meets all other inclusion criteria, then the subject can be included. Genetic mutations will be confirmed by the sponsor's chosen central laboratory. In France, genetic mutations may be confirmed by an approved French organization, in compliance with French legislation prior to Screening Visit 1. Subjects must have (b) seizure onset by 1 year of age and (c) lack of independent ambulation by 2 years of age.
2. Male or female subjects aged 2 through 21 years, inclusive.
3. Subject/parent or LAR willing to give written informed consent/assent, after being properly informed of the nature and risks of the study and prior to engaging in any study-related procedures.
4. Failure to control seizures despite appropriate trial of 2 or more anti-seizure mediations at therapeutic doses.
5. Have at least 16 seizures of primary seizure types: bilateral tonic (sustained motor activity \geq 3 seconds), generalized tonic-clonic, atonic/drop, bilateral clonic or focal to bilateral tonic-clonic per 28 days in each 1-month period in the 2-month period prior to screening.
6. Subject must be approved to participate by sponsor and/or designee (i.e., Epilepsy Consortium) after review of medical history, genetic testing, seizure classification, and historical seizure calendars.

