2.2.2. Secondary Objectives

The secondary objectives of this study are the following:

- To assess behavioral/neuropsychiatric changes correlated with domains of attention, sleep, and a target behavior chosen by the parent/caregiver, using objective tests of CNS function for GNX compared with PBO as adjunctive therapy at the end of the 17-week double-blind phase.
- To assess the safety and tolerability of GNX compared with PBO as adjunctive therapy at the end of the 17-week double-blind phase.
- To assess PK parameters in subjects receiving GNX doses up to 63 mg/kg/day (1800 mg/day maximum) throughout the study.

- To assess the long-term efficacy of GNX when administered as adjunctive therapy throughout the open-label phase.
- To assess the long-term safety and tolerability of GNX when administered as adjunctive therapy throughout the open-label phase.

[REDACTED]

[REDACTED]

- [REDACTED]
- [REDACTED]
- [REDACTED]
- [REDACTED]

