9.7. Efficacy Analyses

All endpoints will be assessed descriptively, by the double-blind treatment to which the subjects are randomized, with point estimates and 95% confidence intervals. Only the primary endpoint will be assessed in an inferential manner since it is unlikely the trial will be powered to achieve statistical significance regarding effects on these measures.

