### 7.1.3.4 Behavioral/Neuropsychiatric Endpoints

The CGICA, CGI-C, and the CGI-I are all 7-point scales, and the number and percentage of subjects with each score will be summarized. The scores range from 1=very much improved and 7=very much worse. (The CGI-I is completed by both parent/caregiver/LAR and clinician.)

[REDACTED]

[REDACTED]

[REDACTED]

[REDACTED]

[REDACTED]

- [REDACTED]
- [REDACTED]
- [REDACTED]

[REDACTED]

[REDACTED]

[REDACTED]

[REDACTED]

[Redacted]

[Redacted]

[Redacted]

[Redacted]

[Redacted]

- [Redacted]

- [Redacted]

[Redacted]

[Redacted]

[Redacted]

[Redacted]

[Redacted]

[Redacted]

[Redacted]

[REDACTED]

- [REDACTED]
- [REDACTED]

[REDACTED]

- [REDACTED]
- [REDACTED]
- [REDACTED]
- [REDACTED]
- [REDACTED]
- [REDACTED]
- [REDACTED]
- [REDACTED]

[REDACTED]

[REDACTED]

[REDACTED]

[REDACTED]

[REDACTED]

[REDACTED]

[REDACTED]

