### **7.1.7 Protections for Multiplicity**

There is a single primary efficacy endpoint, and formal hypothesis testing will not be performed for the other endpoints. Hence no protections for multiplicity are needed.

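### For CSHQ, ADAMS, QI-Disability and PSI the readable SAP gives only unadjusted differences in means; using each subject's baseline score as a covariate would tighten the intervals modestly at almost no cost

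*SAP*

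**What the plan says.** The general rule is in the opening of SAP section 7. For outcomes that are neither seizure-based nor categorical, it takes three quantities (the value before treatment, the value on treatment, and the change) and says that these "will be summarized with 95% confidence intervals for the means and differences in means between the treatment groups". That makes three between-arm contrasts, all unadjusted. No readable part of the SAP names ANCOVA, a baseline covariate or adjusted means. The abbreviation list has ANOVA only, and the code in SAP 12.2 is for seizure endpoints.

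A baseline exists for each scale. SAP 2.1 says: "Baselines for non-seizure efficacy and safety assessments are defined as the last non-missing value of the assessment before the first dose of treatment". Protocol 7.2.1.3, 7.2.2.2 and 7.2.3 place CSHQ, ADAMS, QI-Disability and PSI at Visit 2 before dosing and at Weeks 5, 9 and 17. SAP 7.1.6 repeats the non-seizure analyses at Weeks 5 and 9.

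These endpoints are descriptive. Protocol 9.7 says "Only the primary endpoint will be assessed in an inferential manner", and SAP 7.1.7 that "formal hypothesis testing will not be performed for the other endpoints".

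The global impression scales are handled differently. SAP 7.1.3.4 says: "The CGICA, CGI-C, and the CGI-I are all 7-point scales, and the number and percentage of subjects with each score will be summarized"; SAP 7.1.3.3 does the same for CGI-CSID. They rate change directly and have no baseline score.

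**The concern.** In a randomised trial with a baseline measurement of the same scale, the follow-up value alone and the raw change are two fixed choices of how much baseline to take away: none of it, or all of it. ANCOVA estimates that amount from the data. Under equal standard deviations it has the smallest variance of the three, except at the extremes where it ties with one of them.

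What is at stake is limited but real. Protocol 2.2.2 lists as a secondary objective "To assess behavioral/neuropsychiatric changes correlated with domains of attention, sleep, and a target behavior", and CSHQ is the sleep questionnaire among the instruments. With no test planned, the point estimate and its interval are all that the trial offers on these scales. An interval wider than it need be, around an estimate that moves with a chance baseline difference, weakens that evidence for no benefit.

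**Working it through.** **Inputs from the documents.** 100 subjects, 1:1, so 50 per arm (Protocol 9.5, SAP 1.3.2). Randomisation is stratified on baseline seizure frequency only (Protocol 6.2.2), so it does not directly balance the scale scores.

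**The plan's own figure.** The documents give no SD, effect, power or correlation for these scales, so there is no stated figure to reproduce on this point. The primary-endpoint power does reproduce: difference 30, SD 44.5, one-sided 0.025 gives Φ(30/(44.5·√(2/50)) − 1.96) = Φ(1.41) = 92.1%, against 92% stated. It is used here only to confirm the 50 per arm.

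**Assumptions.** The baseline to follow-up correlation ρ is not in the documents and is shown over a range. SDs are equal at both visits, and all 100 subjects are analysed.

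**Precision.** In units of SD²·(2/n), the variance of the between-arm difference is:

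- follow-up value alone: 1
- change from baseline: 2(1 − ρ)
- ANCOVA: 1 − ρ²

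The follow-up contrast is the better planned one below ρ = 0.5 and the change contrast above it. The fair comparator for ANCOVA is whichever is smaller.

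| ρ | Follow-up | Change | ANCOVA | ANCOVA / better planned | CI narrower by (1 − √ratio) |
|---|---|---|---|---|---|
| 0.3 | 1 | 1.40 | 0.91 | 0.91 | 4.6% |
| 0.5 | 1 | 1.00 | 0.75 | 0.75 | 13.4% |
| 0.7 | 1 | 0.60 | 0.51 | 0.85 | 7.8% |
| 0.8 | 1 | 0.40 | 0.36 | 0.90 | 5.1% |
| 0.9 | 1 | 0.20 | 0.19 | 0.95 | 2.5% |

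Up to ρ = 0.5 the ratio is 1 − ρ², which falls with ρ; beyond it the ratio is (1 + ρ)/2, which rises. The gain therefore peaks at ρ = 0.5.

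With t quantiles and 50 per arm, the 95% half-width for the follow-up contrast is 1.984 × 0.20 = 0.397 SD. For change against ANCOVA the half-widths are 0.470 and 0.381 SD at ρ = 0.3, 0.397 and 0.346 at 0.5, 0.307 and 0.285 at 0.7, 0.251 and 0.239 at 0.8, and 0.177 and 0.174 at 0.9. Allowing for the estimated slope makes the gains slightly smaller than in the table.

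**Chance imbalance.** The baseline difference d has standard error √(2/50) = 0.20 SD, a 95% range of ±0.39 SD. Given d, the expected follow-up difference is the treatment effect plus ρd. Subtracting d shifts the change-score estimate by ρd − d = −(1 − ρ)d, opposite in sign to the imbalance. For d = 0.20 SD this is −0.14, −0.10, −0.06, −0.04 and −0.02 SD at ρ = 0.3, 0.5, 0.7, 0.8 and 0.9. The ANCOVA estimate is not shifted.

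A simulation of 4,000 trials at each of ρ = 0.3, 0.5, 0.7 and 0.9 agrees: the slope of the change-score estimate on d was −0.69, −0.51, −0.30 and −0.10, and that of ANCOVA about 0. Both estimators averaged about zero under no effect.

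**A reason why ρ may be lower for ADAMS.** The baseline form asks about the previous 6 months (Protocol Appendix 9), the later form about the time since the last visit (Appendix 10). Different recall periods could weaken the correlation. Below ρ = 0.5 the change is noisier than the follow-up score alone.

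**The case against.** The strongest case for leaving the plan alone has four parts.

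*The baseline is already used.* A reader might infer from the absence of a covariate that the baseline score is ignored. The documents do not support that: it is subtracted in the change, and any imbalance is displayed by arm with its own interval. The follow-up contrast is also reported and beats the change score at low ρ. This stands, and is why the gain above is measured against the better planned contrast.

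*The estimates are valid.* A reader might call them biased by baseline imbalance. Over randomisation they are not. The shift is conditional on the observed d and is an over-correction. This also stands; the case for adjustment is precision and conditional accuracy.

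*Nothing is tested.* It is tempting to translate the narrower interval into power. The plan runs no test on these scales, so no power claim is warranted and no decision rule or error rate changes. The scales also appear in no readable primary, key secondary or secondary endpoint list. This limits the importance of the point, although with no test the interval is the whole result.

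*The detail is blacked out.* The SAP text between 7.1.3.4 and 7.1.5, where these scales would probably be described, cannot be read. A reader should not infer that the SAP contains no adjusted model. The point rests on what section 7 says, not on what is hidden, and it falls for any scale whose own text already specifies adjustment.

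**Conclusion.** The point holds as a small, inexpensive improvement. The readable rule in SAP section 7 gives unadjusted differences in means where a baseline-adjusted difference would be more precise and would not move with chance imbalance. Against the better planned contrast the interval narrows by at most about 13%, and by roughly 2.5% to 8% if ρ is 0.7 to 0.9.

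This rests on an assumed ρ, equal SDs at the two visits, and the four scales falling under the general rule for non-categorical endpoints. It does not extend to CGICA, CGI-C, CGI-I or CGI-CSID, which have no baseline score, and it does not touch the primary rank test or any error rate.

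**What to change.** In SAP section 7, add for each of CSHQ, ADAMS, QI-Disability and PSI an ANCOVA of the Week 17 score, repeated at Weeks 5 and 9, on treatment, the subject's own baseline score and the randomisation stratum of Protocol 6.2.2. Report the adjusted mean difference with its 95% interval as the main between-arm estimate, and keep the raw baseline, follow-up and change summaries as descriptive. If the blacked-out text already contains such a model, a cross-reference from section 7 is enough.

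The cost is SAP wording and one short model per scale and visit, with no new data. The downside is an assumed roughly linear relation between follow-up and baseline, which robust standard errors can cover.
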